4.3.1.2 Hematological Toxicity

The following hematological toxicity will be considered dose-limiting:

- Grade 4 thrombocytopenia (<25,000/ μ L)
- Grade 4 (<500/ μ L) neutropenia
- Grade 3 (<1000/ μ L) neutropenia associated with fever (Febrile neutropenia) will be considered dose-limiting

4.4 Toxicity Management: Dose Delays and Discontinuation

Dosing with Yttrium-90 will follow standard of care procedures, and there will be no dose modifications.

Any patient who receives at least one dose of nivolumab will be evaluable for toxicity endpoints. Each patient will be assessed for the development of toxicity by laboratory results and physical exam at each study visit, according to CTCAE 4.03.

Nivolumab may be delayed or discontinued following the instructions detailed in section 4.4.1.

In addition, nivolumab should be discontinued for toxicities as outlined in section 4.4.2.

4.4.1 Dosing delays

There will be no dose modifications allowed for management of toxicities.

Patients will be allowed to delay nivolumab treatment by up to 6 weeks.

Nivolumab administration should be delayed for the following until resolution to \leq Grade 1 or baseline:

- Any Grade ≥ 2 non-skin, drug-related adverse event, with the following exceptions:
 - Grade 2 drug-related fatigue or laboratory abnormalities do not require a treatment delay
- Any Grade 3 skin, drug-related adverse event
- Any Grade 3 drug-related laboratory abnormality, with the following exceptions for lymphopenia, leukopenia, AST, ALT, or total bilirubin:
 - Grade 3 lymphopenia or leukopenia does not require dose delay
 - If a subject has a baseline AST, ALT or total bilirubin that is within normal limits, delay dosing for drug-related Grade ≥ 2 toxicity
 - If a subject has baseline AST, ALT, or total bilirubin within the Grade 1 or 2 toxicity range, delay dosing for drug-related Grade ≥ 3 toxicity
 - During Cycle 1, a delay in dosing is not required for Grade 3 total bilirubin ≤ 3.5 mg/dL

NOTE: If bilirubin worsens after the first dose of nivolumab, a delay in dosing may be warranted per physician discretion.

- Any adverse event, laboratory abnormality, or intercurrent illness which, in the judgment of the investigator, warrants delaying the dose of study medication.

Immuno-oncology (I-O) agents are associated with AEs that can differ in severity and duration than AEs caused by other therapeutic classes. Nivolumab is considered an immuno-oncology agent in this protocol. Early recognition and management of AEs associated with immune-oncology agents may mitigate severe toxicity. Management Algorithms have been developed to assist investigators in assessing and managing the following groups of AEs:

- Gastrointestinal
- Renal
- Pulmonary
- Hepatic
- Endocrinopathy
- Skin
- Neurological

The above algorithms are found in the nivolumab Investigator Brochure and appendix 3 of this protocol.

4.4.2 Treatment of nivolumab-related infusion reactions

Since nivolumab contains only human immunoglobulin protein sequences, it is unlikely to be immunogenic and induce infusion or hypersensitivity reactions. However, if such a reaction were to occur, it might manifest with fever, chills, rigors, headache, rash, pruritus, arthralgias, hypotension, hypertension, bronchospasm, or other allergic-like reactions. All grade 3 or 4 infusion reactions should be reported within 24 hours to the study QAM and reported as an SAE if it meets the criteria. Infusion reactions should be graded according to NCI CTCAE (Version 4.03) guidelines.

Treatment recommendations are provided below and may be modified based on local treatment standards and guidelines, as appropriate:

NCI CTCAE Grade	Treatment	Premedication at subsequent dosing

Grade 1 Mild reaction; infusion interruption not indicated; intervention not indicated
	
Remain at bedside and monitor subject until recovery from symptoms.
	
The following prophylactic pre-mediations are recommended for future infusions:
 
 • Diphenhydramine 50 mg (or equivalent) and/or • Acetaminophen/paracetamol 325 to 1000 mg at least 30 minutes before additional nivolumab administrations

Grade 2 Moderate reaction requires therapy or infusion interruption but responds promptly to symptomatic treatment [e.g., antihistamines, non-steroidal anti-inflammatory drugs, narcotics, corticosteroids, bronchodilators, IV fluids]; prophylactic medications indicated for < 24 hours
	
Stop the nivolumab infusion, begin an IV infusion of normal saline, and treat the subject with diphenhydramine 50 mg IV (or equivalent) and/or acetaminophen/paracetamol 325 to 1000 mg;
 
Remain at bedside and monitor subject until resolution of symptoms.
 
Corticosteroid and/or bronchodilator therapy may also be administered as appropriate. If the infusion is interrupted, then restart the infusion at 50% of the original infusion rate when symptoms resolve (please follow stability instructions in section 8.2.4) ; if no further complications
	
For future infusions, the following prophylactic pre-mediations are recommended:
 
 • Diphenhydramine 50 mg (or equivalent) and/or • Acetaminophen/paracetamol 325 to 1000 mg should be administered at least 30 minutes before nivolumab infusions. If necessary, corticosteroids (up to 100 mg of SoluCortef or equivalent) may be used.

NCI CTCAE Grade	Treatment	Premedication at subsequent dosing
	
ensue after 30 minutes, the rate may be increased to 100% of the original infusion rate.
 
Monitor subject closely. If symptoms recur, then no further nivolumab will be administered at that visit.
	

Grades 3 or 4 Severe reaction, Grade 3: prolonged [i.e., not rapidly responsive to symptomatic medication and/or brief interruption of infusion]; recurrence of symptoms following initial improvement; hospitalization indicated for other clinical sequelae [e.g., renal impairment, pulmonary infiltrates]. Grade 4: Life-threatening; pressor or ventilatory support indicated
	
Immediately discontinue infusion of nivolumab. Begin an IV infusion of normal saline and treat the subject as follows: Recommend bronchodilators, epinephrine 0.2 to 1 mg of a 1:1000 solution for subcutaneous administration or 0.1 to 0.25 mg of a 1:10,000 solution injected slowly for IV administration, and/or diphenhydramine 50 mg IV with methylprednisolone 100 mg IV (or equivalent), as needed.
 
Subject should be monitored until the Investigator is comfortable that the symptoms will not recur. Nivolumab will be permanently discontinued. Investigators should follow their institutional guidelines for the treatment of anaphylaxis. Remain at bedside and monitor subject until recovery of the symptoms
 
In case of late-occurring hypersensitivity symptoms (e.g., appearance of a localized or generalized pruritus within 1 week after treatment), symptomatic treatment may be given (e.g., oral antihistamine or corticosteroids
	
No subsequent dosing

4.4.3 Treatment Discontinuation Criteria:

Tumor assessments for all subjects should continue every 8 weeks or 12 weeks once beyond 13 months of therapy, as per protocol, even if dosing is held or delayed.

Nivolumab treatment should be permanently discontinued for the following:

- Any Grade 2 drug-related uveitis, eye pain, or blurred vision that does not respond to topical therapy and does not improve to Grade 1 severity within the re-treatment period OR requires systemic treatment
- Any Grade 3 non-skin, drug-related adverse event lasting > 7 days, with the following exceptions: for laboratory abnormalities, drug-related uveitis,

pneumonitis, bronchospasm, hypersensitivity reactions, infusion reactions, and endocrinopathies:

- Grade 3 drug-related uveitis, pneumonitis, bronchospasm, hypersensitivity reaction, or infusion reaction **of any duration** requires discontinuation
- Grade 3 drug-related endocrinopathies adequately controlled with only physiologic hormone replacement do not require discontinuation
- Grade 3 drug-related laboratory abnormalities do not require treatment discontinuation except:
 - Any Grade 3 drug-related thrombocytopenia > 7 days or associated with bleeding requires discontinuation
- Any drug-related liver function test (LFT) abnormality that meets the following criteria require discontinuation:
 - AST or ALT > 5-10 x ULN for > 2 weeks
 - AST or ALT > 10 xULN
 - Total bilirubin > 5 x ULN
 - Concurrent AST or ALT > 3 xULN and total bilirubin > 2 x ULN
- Any Grade 4 drug-related adverse event or laboratory abnormality, except for the following events which do not require discontinuation:
 - Grade 4 neutropenia ≤7 days
 - Grade 4 lymphopenia or leukopenia
 - Isolated Grade 4 amylase or lipase abnormalities that are not associated with symptoms or clinical manifestations of pancreatitis. The PI and DSMC should be consulted for Grade 4 amylase or lipase abnormalities.
 - Isolated Grade 4 electrolyte imbalances/abnormalities that are not associated with clinical sequelae and are corrected with supplementation/appropriate management within 72 hours of their onset
 - Grade 4 drug-related endocrinopathy adverse events, such as adrenal insufficiency, ACTH deficiency, hyper- or hypothyroidism, or glucose intolerance, which resolve or are adequately controlled with physiologic hormone replacement (corticosteroids, thyroid hormones) or glucose-controlling agents, respectively, may not require discontinuation.
- Any event that leads to interruption in dosing lasting > 6 weeks from the previous dose requires discontinuation, with the following exceptions:
 - Dosing interruptions to allow for prolonged steroid tapers to manage drug-related adverse events are allowed. Prior to re-initiating treatment in a subject with a dosing interruptions lasting > 6 weeks from the previous dose, the PI and DSMC must be consulted. Tumor assessments should continue as per protocol even if dosing is interrupted. Periodic study visits to assess safety and laboratory studies should also continue every 6 weeks or more frequently if clinically indicated during such dosing interruptions.
 - Dosing interruptions lasting > 6 weeks from the previous dose that occur for non-drug-related reasons may be allowed if approved by the PI and DSMC. Prior to re-initiating treatment in a subject with a dosing interruption lasting > 6 weeks, the PI and DSMC must be consulted. Tumor assessments should continue as per protocol even if dosing is interrupted. Periodic study visits to assess safety and laboratory studies should also continue every 6 weeks or more frequently if clinically indicated during such dosing interrupted.

NU Study Number: NU 16101
BMS Study Number: CA 209-615

- Any adverse event, laboratory abnormality, or intercurrent illness which, in the judgment of the Investigator, presents a substantial clinical risk to the subject with continued nivolumab dosing.

4.4.4 Treatment with nivolumab beyond progression

In the event of an initial assessment of PD (based on RECIST Version 1.1), a subject may continue to receive the assigned study treatment as long as none of the criteria listed below are met. Criteria for discontinuation of investigational product include:

- Confirmed PD without clinical benefit: An initial assessment of PD by RECIST Version 1.1 will be confirmed by a repeat evaluation at the next tumor assessment time point, but no sooner than 4 weeks later (see Section 6.3.3 for disease evaluation). Patients with confirmed PD at this time should be discontinued. However, if a patient with confirmed PD is still receiving clinical benefit in the investigator's opinion, study drug may be continued after discussion and agreement between the treating physician and PI.
- Meets any of the other investigational product discontinuation criteria (Section 4.4.3)
- Clinical symptoms or signs indicating significant PD such as the benefit-risk ratio of continuing therapy is no longer justified.
- Decline in ECOG performance status.
- Threat to vital organs/critical anatomical sites (e.g., spinal cord compression) requiring urgent alternative medical intervention, and continuation of study therapy would prevent institution of such intervention.

If the lesions included in the tumor burden subsequently regress to the extent that the criteria for PD are no longer met, then treatment may continue according to the treatment schedule.

4.5 Concomitant Medications/Treatments

Medications or vaccinations specifically prohibited in the exclusion criteria are not allowed during the ongoing trial. If there is a clinical indication for one of these or other medications or vaccinations specifically prohibited during the trial, discontinuation from the trial may be required. The investigator should discuss any questions regarding this with the PI. The final decision on any supportive therapy or vaccination rests with the investigator and /or the subject's primary oncologist. However the decision to continue the patient on trial therapy or vaccination schedule requires the mutual agreement of the Investigator, the study Quality Assurance Monitor (QAM) and the subject.

4.5.1 Acceptable Concomitant Medications

All treatments that the investigator considers necessary for a subject's welfare, with the exception of those listed in section 4.5.2, may be administered at the discretion of the investigator in keeping with the community standards of medical care. All concomitant medication will be recorded on the case report form (CRF) including prescription, over-the-counter (OTC), herbal supplements, and IV medications and fluids. If changes occur during the trial period, documentation of drug dosage, frequency route and date may also be included on the CRF. All concomitant medications received from the time of informed consent until 30 days after the last dose of trial treatment should be recorded. Concomitant medications administered past 30 days after the last dose of trial treatment should be recorded if given in relation to SAEs.

Patients who are on treatment for hepatitis B and C will be allowed to continue their medications while on study with close monitoring from their treating hepatologists.

4.5.2 Prohibited Concomitant Medications

Subjects are prohibited from receiving the following therapies during the Screening and Treatment Phase of this trial:

- Anti-cancer systemic chemotherapy or biological therapy within 28 days of registration.
- Investigational agents within 28 days of study registration.
- Radiation therapy within 14 days of registration
- Live vaccines within 28 days prior to study registration and while participating in the trial. Examples of live vaccines include, but are not limited to, the following: measles, mumps, rubella, chicken pox, yellow fever, rabies, BCG, and typhoid (oral) vaccine. Seasonal influenza vaccines for injection are generally killed virus vaccines and are allowed; however intranasal influenza vaccines (e.g. Flu-Mist®) are live attenuated vaccines, and are not allowed at any time during the study.
- Glucocorticoids for any purpose other than to modulate symptoms from an event of clinical interest of suspected immunologic etiology. However, patients are allowed to use bronchodilators or local steroid injections if clinically necessary.

Subjects who, in the assessment by the investigator, require the use of any of the aforementioned treatments for clinical management should be removed from the trial. Subjects may receive other medications that the investigator deems to be medically necessary.

The Exclusion Criteria describes other medications, which are prohibited in this trial. There are no prohibited therapies during the follow-up phase

4.6 Other Modalities or Procedures

Radioembolization therapy is performed in a two-step process: a diagnostic angiogram and Technetium-99 macroaggregated albumin (⁹⁹Tc-MAA) scan, followed by the treatment session. Y90-specific informed consent will be obtained. Prior to the administration of Y90, a mesenteric angiogram is performed to determine the tumor's blood supply, aberrant anatomy and to ensure proper catheter position. Using a unilateral femoral approach, selective catheterization of the hepatic artery will be performed. Vascular access is obtained via the common femoral artery and a guidewire advanced under fluoroscopic guidance. A 5-F sheath is then inserted over the guidewire. The superior mesenteric artery is selected and an angiogram performed.

4.7 Duration of Therapy

Y-90 will be administered at the start of the study. A single Y-90 treatment will be performed, and nivolumab treatment will start 7-14 days later to allow for full recovery. Additional Y-90 treatments may be allowed after discussion with the principal investigator**.

Subjects will receive study treatment (nivolumab) until disease progression (see section 4.4.3 for details on treatment beyond initial progression), intolerance due to toxicity or withdrawal from the study either by the patient or at the recommendation of the treating oncologist. The study may be stopped sooner, for, toxicity, IRB stopping the study, FDA stopping the study, sponsor stopping the study, principal investigator stopping the study, subject has a positive pregnancy test, use of illicit drugs, non-compliance, deterioration to ECOG level 4, progression of HCC, withdrawal of consent (regardless of reason), variceal bleeding, or death. Patients will be assessed for response by CT scan or MRI every 8 weeks (2 cycles) for the first 13 months, and every 12 weeks (3 cycles) thereafter.

***Repeat therapy to the treated lesion or additional untreated lesions may be warranted. If a patient requires additional Y-90 after starting nivolumab treatment, it may be given once approval from the interventional radiologist and treating physician has been confirmed. In such cases, nivolumab should be held for ≥ 7 days prior to administering Y-90. Nivolumab can be resumed at least 7 days after receiving additional Y-90, and can be delayed for up to 4 weeks if needed.*

4.8 Duration of Follow Up

Once a patient comes off study treatment for any reason other than death, an End of Treatment visit should occur 30 days (+/- 7 days) after the last dose of nivolumab.

Patients will be followed for survival for up to 2 years after treatment discontinuation. If a patient discontinues treatment prior to 24 weeks (6 cycles), they should undergo follow-up (either by routine clinic visit or by phone call) every 2 weeks until the end of the 24-week period from start of study treatment to document survival and disease progression. After this period, patients should be followed for survival every 6 months for 2 years (by routine clinic visit or phone call). Patients should also be followed for SAE's for 100 days after discontinuing study drug.

4.9 Removal of Subjects from Study Treatment and/or Study as a Whole

Patients can be taken off the study treatment and/or study at any time at their own request, or they may be withdrawn at the discretion of the investigator for safety, behavioral or administrative reasons. The reason(s) for discontinuation will be documented and may include:

- Any event which, in the opinion of the investigator/sub-I's opinion, requires termination of the study/study medications (including non-compliance)
- At the request of the subject (Withdrawal of consent)
- At the request of a regulatory body (FDA, NU IRB)
- Patients with a positive beta-HCG test (consistent with pregnancy)
- Use of illicit drugs or other substances that may contribute to toxicity
- Deterioration of PS to ECOG 4
- Progression of disease, as evidenced by radiologic progression and/or clinical status is worsening, subject not benefiting from the study drug.
- Development of a second cancer
- Subject is lost to follow-up
- More than two Y-90 treatments
- Grade 4 hyperbilirubinemia (high bilirubin) defined by the Common Terminology Criteria for Adverse Events (CTCAE) version 4.03 of bilirubin more than 10 times the upper limit of normal,
- The Northwestern University Institutional Review Board/Office for the Protection of Research Subjects (offices at Northwestern that protects study patients) stops the study.
- Death

The study will be stopped if 2 of the first 5 patients receiving (Y-90 + nivolumab) develop grade 4 hyperbilirubememia (>10) OR a death occurs believed to be related to therapy and not due to the natural progression of liver disease and liver cancer.

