4.2.2 Nivolumab

For the first 3 patients in Phase I, nivolumab will be administered at 80mg as an intravenous infusion over approximately 30 minutes (-5 minutes / +15 minutes) every 2 weeks (Day 1 & 15 of each cycle) until disease progression or intolerable toxicity.

Dose escalation to 240mg will be determined in the standard 3+3 fashion (detailed in section 4.3). All patients in Phase Ib will be treated at 240mg IV nivolumab if determined to be the MTD. Treatment will begin 7-14 days after Y-90 administration. Patients should have recovered from any side effects resulting from Y-90 treatment (to ≤G1 or baseline). If a patient is still experiencing side effects 14 days after Y-90 treatment, the patient’s nivolumab treatment may be delayed by up to 14 additional days at the physician’s discretion (maximum 4-week delay). Scans will need to be performed 21-28 days after Y-90 administration, and will fall during Cycle 1 of nivolumab. If a patient is not able to start nivolumab treatment within 4 weeks (28 days), the patient should come off study and be replaced.

Subjects may be dosed no less than 12 days from the previous dose. There are no pre-medications recommended for nivolumab on the first cycle. If an acute infusion reaction is noted, subjects should be managed according to Section 4.2.4.

Treatment will be administered on an outpatient basis. Reported adverse events and potential risks are described below. No investigational or commercial agents or therapies other than those described below may be administered with the intent to treat the patient’s malignancy.

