4.3 Phase I Dose Escalation Scheme

In this phase 1/1b pilot study, the dose escalation component will be for nivolumab, starting at a dose of 80mg. Please see the table in statistical section for dose adjustments.

Phase I Dose Escalation Plan based on 3+3 design:

Dose Level	Nivolumab
1	80mg IV every 2 weeks
2	240mg IV every 2 weeks

NU Study Number: NU 16101
BMS Study Number: CA 209-615

A standard “3+3” dose escalation design will be utilized. Initially, 3 patients will be enrolled at the starting dose (level 1), after which enrollment will be temporarily suspended until all 3 patients complete the DLT evaluation period (defined as cycle 1 or the first 28 days of treatment). Once all 3 patients complete the DLT period and toxicity data has been submitted, the Data and Safety Monitoring Committee (DSMC) will review the data and confirm the presence or absence of any DLTs (defined below). The following rules will be used at each dose level to determine whether or not to proceed to the next dose level:

- If 0 of 3 patients at a given dose level experience a DLT (defined below), then escalation will proceed to the next dose level.
- If 2 or 3 of 3 patients at a given dose level experience a DLT, then one of the following must occur:
 - If this happens at level 1, the PI will discuss with DSMC and BMS to determine the necessary outcome.
 - If this happens at level 2 or beyond, the previous level will be declared the maximum tolerated dose (MTD).
- If 1 of 3 patients at a given dose level experiences a DLT, then an additional 3 slots will be added (for a total of 6 patients at that level):
 - If 1 of 6 total experiences a DLT, then escalation will proceed to the next level.
 - If ≥ 2 of 6 total experience a DLT, the previous level will be declared the MTD.

NOTE: Whichever dose level is declared the MTD must have 6 total patients treated at that level. For example, if 3 patients are treated at level 2 and 0 patients experience DLT, escalation would then proceed to level 3. However, if ≥ 2 patients at level 3 experience DLT, enrollment to level 2 would need to be re-opened to enroll an additional 3 patients at that level (with 0 or 1 DLT observed in 6 total patients) in order to declare level 2 the MTD.

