4.3.1 Definitions

DLT is defined as a significant adverse events (detailed below) occurring during the DLT period (first 28 days of nivolumab treatment) that is related to nivolumab. DLT will be evaluated according to CTCAE v 4.03 criteria. Delay in starting nivolumab therapy more than 2 weeks due to toxicity regardless of attribution or grade, is considered a DLT

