4.3.1.1 Grade ≥ 3 non hematological toxicity

Grade ≥ 3 non-hematological toxicity felt to be related to study medication will be considered dose-limiting with the following clarifications:

- Diarrhea Grade 3 will only be considered dose limiting if it is refractory to treatment as outlined in the supportive care guidelines (section 4.4.3)
- Bloody or grade 4 diarrhea will be considered dose limiting
- Nausea or vomiting grade 3 will only be considered dose limiting if it is refractory to anti-emetic therapy and unable to be corrected to \leq Grade 1 within 24 hours
- Rise in serum creatinine to grade 3, not corrected to \leq grade 1 within 24hrs with IV fluids will be considered dose limiting
- Grade 3 metabolic toxicities unable to be corrected \leq grade 2 within 24 hours (like glucose changes, hypokalemia, hypomagnesaemia, hypophosphatemia, and hyponatraemia) will be considered dose limiting, unless patient had metabolic abnormalities at baseline. Grade 4 metabolic toxicities that are symptomatic will be considered dose-limiting regardless of duration or ability to correct.
- Other Grade 3 lab abnormalities will only be considered a DLT if they do not resolve within 2 weeks.
- Elevated bilirubin will not be considered a DLT unless >3.5 mg/dL

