8.2.5 Protocol dose specifics

The first 3 patients in Phase I will be dosed at 80mg q2weeks. Patients will then be dosed at 240mg q2weeks, and the study will continue into Phase Ib provided 240mg is the MTD.

Nivolumab is to be administered as an approximately 30-minute IV infusion, using a volumetric pump with a 0.2 - 1.2 micron in-line filter at the protocol-specified dose. The drug can be diluted with 0.9% Sodium Chloride or 5% Dextrose for delivery with minimum allowable concentration of 0.35% mg/mL. It

is not to be administered as an IV push or bolus injection. At the end of the infusion, flush the line with a sufficient quantity of normal saline.

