10.0 STATISTICAL CONSIDERATIONS

10.1 Study Design/Study Endpoints

This is a single-center Phase I/Ib study aiming to evaluate the safety, efficacy, and tolerability of nivolumab combined with therasphere, Y-90, in patients with advanced hepatocellular carcinoma.

The expected number of patients on dose escalation will be in the range of 9-15 based on the 3+3 design. Six patients will be treated at the MTD in the dose escalation phase. The dose calculation for Yttrium-90 Therasphere will be done according to standard protocol at Northwestern Memorial Hospital. Please note - details of this are located in section 8.1.

Phase Ib Expansion Cohort:

A Simon two stage optimum Phase II design (1989) will be used to test the null hypothesis that the response rate is 10% versus an alternative hypothesis of 30 [36]. Up to 29 evaluable patients will be entered into Phase 1b. The 6 patients at the MTD in Phase 1 will be counted as part of the 29 in Phase 1b. In the first stage, 10 patients will be entered. If none or 1 show a response, then consideration will be given to trial termination due to inactivity of the treatment. If 2 or more of 10 show a response, then an additional 19 patients will be added. If 5 or fewer of 29 show a response, then the trial will conclude that the response rate could be as low as 10%. If 6 or more respond, then the trial will conclude that the response rate is greater than 10%. This design has a 20% chance of falsely concluding the rate is 10% (Type II error = 20%), and a 5% chance of falsely concluding that the rate is greater than 10% (Type I error = 5%). There is a 74% chance that the trial will show 0 or 1 responses in the first stage if the true response rate is 10%.

For the total sample size, Phase 1 requires 9-15 patients, Phase 1b requires 29 patients in a two-stage optimum Simon design. The 6 at the MTD in Phase 1 are counted as part of the 29. This would require up to 15 in Phase 1, 23 new patients in Phase 1b for a total of 38 patients. Target accrual is 40 patients to account for potentially unevaluable patients.

Treatment duration:

Treatment will continue until disease progression (imaging done every 8 weeks), intolerable side effects, or patient withdraws consent or is removed from the study for any other reason.

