1.3.1 (Rationale for Nivolumab Dosing)	n/a	Adds justification for the dose escalation from 80mg to 240mg IV nivolumab, indicating that nivolumab is now FDA-approved at 240mg	Additional information provided to justify stopping escalation at 240mg nivolumab.
3.1.9 (Inclusion Criteria)	
 n/a Included screening requirements for lipase, amylase, and magnesium 	
 Adds note to PT/INR requirement: "Performed at time of screening angiogram; can be outside 14 days if applicable." Removes screening requirements for lipase, amylase, and magnesium 	
 Clarification requested by study team. Clarification to fix discrepancy – screening chemistry panel does not include lipase, amylase, or magnesium
3.2.24 (Exclusion Criteria)	Excluded patients with hypertension (>150/90) and cardiac arrhythmia	No longer excludes cardiac arrhythmia and removes numerical value for hypertension.	PI determined that these exclusion criteria were not clinically relevant or necessary.
4.1 (Overview); 4.2.2 (Nivolumab); 5.0 (Study Procedures #10)	Nivolumab was to be given over 30 minutes with a window of ±5 minutes	The window for nivolumab infusion has been extended to - 5 minutes / +15 minutes	BMS approved this extension in order to allow greater flexibility in infusion times.
4.3.1.1 (Grade ≥3 non-hematological toxicity)	Grade ≥ 3 metabolic toxicities unable to be corrected within 24 hours were considered dose-limiting	Adds an exception if patient had metabolic abnormalities at baseline. Also adds: "Other Grade 3 lab abnormalities will only be considered a DLT if they do not resolve within 2 weeks"	Clarifications. Patients with metabolic abnormalities at baseline are allowed more flexibility. Grade 3 lab abnormalities were not previously accounted for outside of metabolic abnormalities
4.3.1.1 (Grade ≥3 non-hematological toxicity); 4.4.1 (Dosing delays)	Dose delays and DLT's were to take place for any bilirubin abnormality ≥Grade 3	Grade 3 bilirubin ≤3.5mg/dL is not considered dose limiting and does not require delay during Cycle 1. However, if bilirubin worsens after the first dose of nivolumab a delay in dosing may be warranted per physician discretion.	Patients often experience elevated bilirubin as a result of Y-90; a cut-off of 3.5mg/dL is felt to be appropriate during cycle 1, with criteria being more strict

NU Study Number: NU 16101
BMS Study Number: CA 209-615

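### The only study-level count for non-fatal severe liver toxicity (4.9) covers the first 5 patients, so no number in the protocol pauses the 240 mg expansion

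*Combined protocol and SAP*

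**What the plan says.** Section 4.9: "The study will be stopped if 2 of the first 5 patients receiving (Y-90 + nivolumab) develop grade 4 hyperbilirubememia (>10". The same sentence adds a stop for a death attributed to therapy, with no first-5 limit.

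Dose of the first patients, 4.2.2: "For the first 3 patients in Phase I, nivolumab will be administered at 80mg as an intravenous infusion". Section 4.3 escalates after 0 of 3 DLTs, but "If 1 of 3 patients at a given dose level experiences a DLT, then an additional 3 slots will be added". Whichever level becomes the MTD must have 6 patients.

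What counts as a DLT, 4.3.1: an event "occurring during the DLT period (first 28 days of nivolumab treatment) that is related to nivolumab". A toxicity-related delay of more than 2 weeks in starting nivolumab also counts, whatever its attribution. Section 4.3.1.1 speaks of toxicity related to study medication and adds: "Elevated bilirubin will not be considered a DLT unless >3.5 mg/dL". The rationale for that cut-off in Appendix 5 (Amendment 2) is: "Patients often experience elevated bilirubin as a result of Y-90".

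Expansion, 8.2.5: "the study will continue into Phase Ib provided 240mg is the MTD". Section 10.1 counts the 6 Phase I patients at the MTD among the 29, which leaves "23 new patients in Phase 1b for a total of 38 patients". Its only interim rule in Phase Ib concerns responses (0 or 1 of 10).

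Safeguards without a study-level number:
- individual discontinuation (4.4.3, 4.9)
- 24-hour SAE reporting and DSMC review (7.3.3.1)
- potential drug-induced liver injury reported as an SAE (7.2.12)
- High Intensity Monitoring under the DSMP (7.0, 11.7)
- a general power to stop for toxicity (4.7)

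**The concern.** The sponsor treats Grade 4 bilirubin as serious enough to stop the study, yet the count closes before most patients at 240 mg are treated. Five patients cannot exclude a high rate, and the 3+3 window is 28 days. Later events in the expansion, including any after the repeat Y-90 that 4.1 and 4.7 allow, fall under no stated number.

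The population makes this more than formal. Sections 3.1.2 and 3.1.9 admit infiltrative disease and bilirubin up to 3 times ULN. Section 8.1.9 lists infiltrative tumor and bilirubin above 2 mg/dL among five risk factors associated with 11 of 12 deaths possibly related to the device.

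The point does not depend on toxicity rising with nivolumab dose. Sections 1.2.2 and 1.3.1 describe no such pattern for nivolumab alone.

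**Working it through.** **1. The plan's own figures reproduce.** New Phase Ib patients: 29 − 6 = 23. Total: 15 + 23 = 38. Simon early stop at a 10% response rate: 0.9^10 + 10 × 0.1 × 0.9^9 = 0.349 + 0.387 = 0.736 (stated 74%). Exact type I error is 0.047 (stated 5%) and power at 30% is 0.805 (stated 80%).

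**2. Who is in the first 5.**
- 0 of 3 DLTs at level 1: doses are 80, 80, 80, 240, 240, so 2 patients are at 240 mg.
- 1 of 3 DLTs at level 1: patients 4–6 also receive 80 mg, so none of the first 5 is at 240 mg.
- Phase I has at least 3 + 6 = 9 patients before expansion, so none of the 23 is counted.

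**3. The 4.9 count alone.** Let p be the Grade 4 bilirubin rate, equal at both doses (assumption). The documents give no value; 10%, 20% and 33% (1/3) are scenarios. P(fires) = 1 − (1−p)^5 − 5p(1−p)^4.
- 10%: 1 − 0.590 − 0.328 = 0.081
- 20%: 1 − 0.328 − 0.410 = 0.263
- 33%: 1 − 0.132 − 0.329 = 0.539

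**4. The 4.9 count and the 3+3 together.** Suppose first that every Grade 4 event is a DLT and that no other DLTs occur. With q = 1 − p, expansion at 240 mg is reached with probability [q^3 + 3p·q^5] × [q^6 + 6p·q^5]. The first bracket is passing level 1; the second is 0 or 1 DLT in 6 at level 2. The 4.9 count then adds nothing, because those paths never have 2 events in the first 5.
- 10%: 0.906 × 0.886 = 0.803, so expansion is prevented in 20%
- 20%: 0.709 × 0.655 = 0.464, prevented in 54%
- 33%: 0.428 × 0.351 = 0.150, prevented in 85%

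If only half of Grade 4 events qualify as DLTs (assumption), simulation of 1,000,000 trials gives 11%, 34% and 65%.

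**5. What a count over the 29 patients at 240 mg would add.** Limits tested: 2 of the first 5, 3 of the first 10, 4 of the first 16, 5 of the first 22, 6 of the 29. An exact patient-by-patient recursion on the 29 alone gives firing probabilities of 0.033 at 5%, 0.167 at 10%, 0.655 at 20% and 0.971 at 33%. Restricted to simulated trials that reach expansion:

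| True rate | Half of Grade 4 are DLTs | All are DLTs |
|---|---|---|
| 10% | 13% | 8% |
| 20% | 59% | 49% |
| 33% | 95% | 92% |

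These figures include limits reached within the first 6 patients at 240 mg. Counting only limits met after the sixth changes the half column to 11%, 58% and 95% and leaves the other unchanged.

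**6. Order of counting.** Take the 29 alone, one patient per 2.17 weeks (2 per month, section 3.0), with events spread evenly over 24 weeks (assumption). At a 20% rate, accrual pauses before patient 29 with probability 0.563 if events are counted by order of treatment, against 0.378 if counted by the number treated when the event occurs.

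**The case against.** **The 3+3 does much of the work.** It screens the 6 patients at 240 mg at a bilirubin limit (above 3.5 mg/dL) well below Grade 4 (above 10 times ULN). A reader might take the 26% in step 3 as the whole protection at a 20% rate. The documents do not support that: 4.9 and the 3+3 together prevent expansion in 34% to 54% of such trials, and more if rises between 3.5 mg/dL and Grade 4 also count. Likewise, 23p (2.3, 4.6 and 7.7 events) describes only a trial that reaches expansion and enrolls all 23. This objection stands as to size. It does not touch the expansion, where the 3+3 no longer applies.

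**Oversight exists.** A reader might infer that the expansion has no safety monitoring. It has individual stopping limits, SAE and liver-injury reporting, DSMC review and the power to stop for toxicity. The related-death limb carries no first-5 limit and needs no change. What is missing from the protocol is a number, and the DSMP, which is not included, may supply one.

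**Y-90 attribution.** A reader might conclude that a bilirubin rise attributed to Y-90 can never be a DLT. The text is ambiguous: 4.3.1 says related to nivolumab, while 4.3.1.1 says study medication. The 3.5 mg/dL allowance, made because Y-90 raises bilirubin, suggests such rises were thought capable of counting.

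**The scenarios are not anchored.** Appendix 1 lists elevated bilirubin at 10% for Y-90, without a grade. Grade 4 rates of 20% and 33% would be high against that, although Y-90 alone does not bound the combination. At 10% the added count gives a modest gain.

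**Conclusion.** The gap is real but limited. Followed exactly, the stated rules leave the 23 new patients outside the sponsor's own Grade 4 bilirubin trigger, and no other number in the protocol pauses their accrual. If the true rate were 20% or more, existing rules would prevent expansion in 34% to 85% of trials across the scenarios. Of those that went ahead, about half or more (49% to 95%) would meet the limits tested here.

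This rests on equal rates at both doses, independent patients, the assumed share of Grade 4 events that are DLTs, and a protocol read without the DSMP. It is a change the sponsor should make. It does not show that the trial is unmonitored or that the rate is high. Confidence is medium, mainly because the DSMP could already contain a limit.

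**What to change.** Keep both existing stops in 4.9 and add: *Among patients treated at 240 mg, through all 29, new accrual is suspended pending DSMC review if Grade 4 bilirubin, attributed to Y-90 or nivolumab and not to progression of liver disease or cancer, occurs in 2 of the first 5, 3 of the first 10, 4 of the first 16, 5 of the first 22 or 6 of the 29, counted by order of treatment.* The sponsor may instead derive limits from a stated acceptable rate, or cite the DSMP limit if one exists.

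Cost: one paragraph and no extra tests, since total bilirubin is already drawn before each dose (5.0) and the collection periods in 7.2.5 can be used. On the 29 alone, the chance of an unneeded pause is 3% at a 5% rate and 17% at a 10% rate. The Simon response limits stay as they are. A safety stop can only lower the chance of declaring activity, so the type I error does not rise above 0.047. Power is kept only if every pause ends in resumption; some is lost if a pause leads to termination.
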